**The specific aims of the present project are therefore to:**

- I. Examine whether the level of a variety of biomarkers at admission are associated with length of hospital stay, time to first readmission within 90 days, and time to mortality within 90 days in old patients, and whether the combination of clinical and functional measures with these biomarkers can identify patients at risk of prolonged hospital stay, readmissions and mortality. Primary end-point is length of stay. Secondary end-points are time to first readmission, time to mortality, muscle mass, muscle strength and frailty score (WP1).
- II. Establish biomarker assays for predicting muscle loss and loss of function in old patients hospitalized at a geriatric ward, assessing whether levels of a variety of biomarkers combined with clinical and functional measures are associated with length of hospital stay, readmissions, mortality and whether patients are discharged to a higher level of care. Primary end-points are the relative change in muscle mass, muscle strength and muscle function. Secondary end-points are length of stay, time to first readmission, time to mortality, frailty score and discharge to a higher level of care (WP2)

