A decrease in hormone concentrations appears to be associated with the development of sarcopenia. Especially in men, the decline in testosterone levels seems to be associated with a decline in muscle mass and muscle strength (39). Indeed, testosterone can increase protein synthesis in muscle and promote muscle regeneration by activating satellite cells (40). Estrogen may also promote muscle repair by activation and proliferation of satellite cells via the estrogen receptor  $\alpha$  and  $\beta$  (41, 42). In addition, a murine study showed that ovariectomized rats (OVX) was unable to fully regain their muscle mass following a period of hindlimb unloading with a subsequent period of reloading compared to OVX rats with estrogen supplementation (43). The protective effect of estrogen on muscle mass during hindlimb unloading and reloading was also confirmed in a study of male rats (44) As such, estrogen might attenuate the degree of disuse atrophy.

Studies have demonstrated that ageing is accompanied by modifications of the immune system, specifically immunosenescence, leading to cytokine dysregulation and a chronic low-grade inflammation (45, 46). This has potential detrimental consequences, as research has shown that biomarkers of inflammation are associated with the pathology of the most common chronic age-related diseases including atherosclerosis (47), chronic heart failure (48), osteoporosis (49), type II diabetes mellitus (50), neurodegenerative disorders (51,52)

and sarcopenia (53, 54, 55). Several studies have investigated the association of inflammatory biomarkers with muscle mass, muscle strength and muscle function. In vitro, exposure of myoblasts to TNF- $\alpha$  inhibits muscle differentiation and causes a decrease in protein synthesis (56). In addition, TNF- $\alpha$  binding to its receptor TNFR activates the NF- $\kappa$ B pathway causing proteolysis (57). However, results regarding the effect of inflammatory biomarkers on muscle mass are inconsistent and lack clear evidence as to whether these inflammatory biomarkers are associated with sarcopenia.

Many studies have assessed low-grade inflammation by measuring a limited number of inflammatory proteins, and one study showed that elderly individuals exhibiting high levels of pro-inflammatory cytokines also tended to show high levels of anti-inflammatory cytokines (58). Thus, we aim to include a variety of both pro- and anti-inflammatory markers.

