Furthermore, distinct patient populations with co-existing pathophysiological processes might exhibit different biomarker profiles. A recent study found a negative association between systemic levels of CRP and changes in muscle mass in geriatric patients in response to resistance training during hospitalization, indicating that patients with inflammation during their hospital stay may have an increased risk of deconditioning during hospitalization (59).

Regardless, systemic levels of the inflammatory marker C-reactive protein (CRP), has been found to be predictive of both the length of hospital stay and readmissions (60, 61). Indeed, geriatric patients with inflammation at admission stayed on average 3 days longer than patients without inflammation, evaluated by CRP levels at admission (62). Despite CRP being a nonspecific marker of inflammation, it has also been recognized as a predictive marker of in-hospital mortality in elderly patients admitted to the acute ward (63).

Recently, suPAR was established as a biomarker of inflammation and immune activation, and elevated levels of suPAR are believed to reflect a state of chronic inflammation (64). suPAR correlates with other inflammatory markers, such as TNF- $\alpha$ , and patients with the highest levels of suPAR generally have the worst prognosis (65). Elevated levels of suPAR have been associated with increased risk of cardiovascular disease, cancer, type II diabetes and premature mortality in the general population, independent of CRP levels (66). However, a recent study found that the prognostic capability of suPAR did not affect all-cause mortality in patients admitted to the emergency department (67).

In a study of HIV-infected patients, suPAR was associated with low muscle mass, while IL-6 was associated with both low muscle mass and increased fat mass in both patients and healthy controls (68). Thus, there seem to be distinct inflammatory processes occurring simultaneously with different effects on muscle mass and fat mass, respectively.

Further validation needs to be conducted in different patient populations to utilize the possible prognostic value of these biomarkers, either individually or in combination with functional and clinical measures.

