### **WP1: Biomarkers in the acutely ill older patient**

**Hypothesis:** We hypothesize that combining clinical and functional measures with systemic biomarkers has the potential to identify older acutely ill medical patients at risk of prolonged (>96 hours) hospital stays, non-elective readmissions, and mortality.

**Overview of Actions:** Acutely ill medical patients (age >65 years) referred to Bispebjerg-Frederiksberg Hospital will consecutively be enrolled in the study. We will recruit participants during a 1-year period.

**Assessments:** Blood tests, frailty (CSHA Clinical Frailty Scale), risk of pressure ulcers (Braden Score), sarcopenia (SARC-F), hand-grip strength, chair-rise test and body composition (BIA). Blood samples will be used to assess biomarkers of muscle atrophy and wasting (GDF-11 & GDF-15), inflammatory cytokines and acute-phase proteins, sex hormones and immune activation (suPAR). All assessments will be performed within the

first 24 hours of admission. Primary endpoint is length of hospital stay. Secondary endpoints are time to first non-elective readmission, time to mortality, muscle strength, muscle mass and frailty.

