All subjects will have blood tests performed to evaluate levels of GDF11 & GDF15, inflammatory cytokines and acute-phase proteins, sex hormones and immune activity (suPAR). In addition, all subjects will have their hand-grip strength, chair-rise ability and body composition (BIA) assessed. Their frailty score and risk of pressure ulcers will be assessed by the CHSA Clinical Frailty Scale and Braden score, respectively. The Charlson Comorbidity Index will be used to assess comorbidity, SARC-F will evaluate the presence of sarcopenia and the Orientation-Memory-Concentration test (OMC) will evaluate cognitive function in all subjects

Subjects included in WP2 will have an additional geriatric assessment including the Barthel Index and De Morton Mobility Index (DEMMLI), which are already part of standard clinical practice. Functional status will additionally be evaluated by a gait-speed test.

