### **Overall outcome analysis**

To test whether clinical, functional and biological biomarkers are associated with length of stay we will perform multivariate logistic regression and to test whether clinical, functional and biological biomarkers are associated with loss of muscle mass and function we will perform multivariate linear regression. To evaluate the prognostic abilities of biomarkers (individual, in combination and combined with clinical and functional measures) we will use area under the curve for receiver operating characteristics (AUROC) statistics.

Table of summary statistics will be presented with a number of baseline variables (age, sex, functional measures, results of blood tests, comorbidities).

Continuous variables will be summarized with: n (non-missing sample size), mean, standard deviation, median, interquartile range, number of missing values. Categorical variables will be reported as frequency and percentages (based on non-missing sample size) and number of missing values.

Continuous and ordinal variables will be tested by Wilcoxon analysis for differences between groups. Categorical variables will be tested with chi-square. Missing data will be imputed.

A reference group of 2058 patients over the age of 65 from Bispebjerg-Frederiksberg University Hospital and Herlev-Gentofte Hospital had a mean age of 78.3 years and a mean length of stay of 5.8 days during hospitalization. 817 of these patients (39.7%) had a prolonged length of stay, defined as a hospitalization lasting more than 96 hours.

With a sample size of 1100 and the assumption that approximately 40% of old medical patients have a prolonged hospital stay, an AUROC of 82 will have a power of 0.9 and a significance level of 0.05. The primary outcome will be mean length of stay. Patients will be grouped in either normal or extended length of stay (<96 hours) and Cox regression analysis will be used to compare differences in readmission and mortality. To assess the discriminative ability of biomarkers with regards to extended length of stay, we will use the area under the curve (AUC) for receiver operating characteristics (ROC) curves. AUCs for different ROC curves will be compared using the DeLong test.

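### DeLong is the only test named for comparing ROC curves: on fitted nested models its error rate is wrong, and fitted AUROCs get no optimism correction

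*Combined protocol and SAP*

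**What the plan says.** In the combined protocol and SAP, the section Overall outcome analysis sets three levels of AUROC evaluation: "To evaluate the prognostic abilities of biomarkers (individual, in combination and combined with clinical and functional measures) we will use area under the curve". The same section later adds "AUCs for different ROC curves will be compared using the DeLong test". It does not say which curves form a pair, or whether the scores are raw markers or predictions from a fitted model. It names no other test for comparing curves. Logistic regression is planned there for association with length of stay, and is the natural source of any combined score.

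Other sections point towards combined models. Aim I asks "whether the combination of clinical and functional measures with these biomarkers can identify patients at risk of prolonged hospital stay". The WP1 hypothesis is that "combining clinical and functional measures with systemic biomarkers has the potential to identify older acutely ill medical patients at risk of prolonged" stays. The Biomarkers section speaks of prognostic value "either individually or in combination with functional and clinical measures".

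The panel is left open: "we aim to include a variety of both pro- and anti-inflammatory markers". No section plans a bootstrap, cross-validation, hold-out sample or shrinkage. Imputation of missing data is planned, without a method.

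**The concern.** DeLong treats each patient's score as given. A combined score is not given: its coefficients are estimated from the same patients in whom the AUROC is then computed. If one fitted model contains the other and the added markers are useless, the two true scores coincide. The fitted larger model still tends to show a higher AUROC, because it has been tuned to these data. The DeLong statistic then no longer has a standard normal distribution.

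The three levels are nested whenever a level keeps the markers of the level before it: a marker against a combination containing it, or a combination against the same combination plus clinical and functional measures. At stake is the statement that biomarkers do or do not improve discrimination, which would depend partly on how many were entered. Separately, AUROCs of fitted models would be apparent values, whichever pairs are compared.

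**Working it through.** **1. The plan's own AUROC figure.** The plan states AUROC 0.82 (printed as 82), power 0.9, level 0.05, n=1100 and 40% prolonged stay, so 0.40 × 1100 = 440 against 660 patients. The Hanley-McNeil variance is [A(1−A) + (n₁−1)(Q₁−A²) + (n₀−1)(Q₂−A²)]/(n₁n₀), with Q₁ = A/(2−A) and Q₂ = 2A²/(1+A).
- At A = 0.82: Q₁ = 0.6949, Q₂ = 0.7389, A² = 0.6724. Variance = (0.148 + 439 × 0.0225 + 659 × 0.0665)/290,400, so SE = 0.0136.
- At A = 0.5: SE = 0.0178.
- Against 0.5, two-sided: z = (0.32 − 1.96 × 0.0178)/0.0136 ≈ 20.9, so power is above 0.999.

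A power of 0.9 needs an unstated fixed null of about 0.773, or a paired comparator AUROC of about 0.753 to 0.800 (correlation 0 to 0.9). The figure cannot be reproduced without a comparator, so it does not reveal which curves are meant. Nothing below rests on it.

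**2. Inputs for the simulation.** From the plan: n=1100, 40% events, and 200 patients in WP2. The Subjects section gives eight clinical or functional measures for everyone: "all subjects will have their hand-grip strength, chair-rise ability and body composition (BIA) assessed", plus the Clinical Frailty Scale, Braden, Charlson, SARC-F and OMC. The documents name about eight markers, some only as background: GDF11, GDF15, suPAR, CRP, TNF-alpha, IL-6, testosterone and estrogen. Assumed: standard normal predictors, independent unless stated, and a base-model AUROC of about 0.63 to 0.81. There were 1000 to 2000 runs for most null settings. With 2000 runs the Monte Carlo SE at 5% is √(0.05 × 0.95/2000) ≈ 0.5 points.

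**3. Tests.** DeLong: z = (A₁ − A₀)/√(Var A₁ + Var A₀ − 2 Cov), two-sided at 1.96. Likelihood ratio: 2(ℓ₁ − ℓ₀) against chi-square with k degrees of freedom, where k is the number of added markers.

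**4. Control.** For two raw markers with equal true AUROC, DeLong rejects 4.5% to 5.8%. It is sound there.

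**5. Useless markers added to a fitted base model, n=1100, nominal 5%.** Ranges cover repeat runs and varied settings.

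| Markers added | DeLong rejects |
|---|---|
| 1 | 0.0–0.1% |
| 3 | 0.2–0.3% |
| 5 | 2.0–2.9% |
| 6 | 3.8% |
| 7 | 5.5% |
| 8 | 6.9–8.6% |
| 10 | 14.0–17.4% |

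The low end at eight markers is with predictors correlated 0.2. The likelihood-ratio test rejects 4% to 6% across the settings in which both were run. The mean DeLong z, which should be 0, is 0.37, 1.00 and 1.49 with 1, 5 and 10 markers (eight-predictor base, AUROC about 0.79). That drift explains the change of direction.

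**6. A nested pair inside the plan's own three levels.** One useful marker against a fitted combination of eight containing it, the other seven useless: DeLong 5.8% to 8.1%, likelihood ratio 4.9% to 6.1%. With only one useless marker added: DeLong 0.05% to 0.2%.

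**7. Power, eight-predictor base.**
- One real marker added alone, odds ratio 1.22 per SD (log-odds ratio 0.20): DeLong 12.9% to 16.7%, likelihood ratio about 81% to 82%. The true AUROC gain is 0.004 (0.761 to 0.765).
- Odds ratio 1.28: 33% against 94%, gain 0.007.
- In a block of eight with one, two or three real markers: 45% against 49%, 78% against 85%, 92% against 97%.

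**8. Optimism in the AUROC difference, eight useless markers.**

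| n | Apparent | Bootstrap-corrected | True in new patients |
|---|---|---|---|
| 1100 | +0.0039 | −0.0037 | −0.0038 |
| 200 | +0.0211 | −0.0107 | −0.0186 |

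At n=200 the bootstrap removes 0.0211 + 0.0107 = 0.0318 of a total optimism of 0.0211 + 0.0186 = 0.0397, about 80%.

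**The case against.** The strongest reply is that the damaging comparison is not in the plan. The three levels all contain biomarkers; no curve for clinical and functional measures alone is listed. The sentence just before the DeLong sentence concerns the discriminative ability of biomarkers, and comparing raw markers with each other is where DeLong works. A reader might infer that the plan commits to testing clinical measures against the same measures plus biomarkers. The aims and the hypothesis speak of what the combination can identify, not of its gain over a clinical-only model, so that stronger reading is not supported.

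The size can also be disputed. Near eight markers the error is modest. For a marker combination against the same plus eight clinical measures, a null of no effect is implausible. With an assumed marker log-odds ratio of 0.15 and clinical log-odds ratio of 0.10, DeLong rejects 88% against 92% for the likelihood ratio; at 0.15 and above for the clinical measures both reach 100%. The single marker that DeLong misses is worth only 0.004 in AUROC.

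All of this stands as a limit on weight. It does not remove the point. A marker against a combination containing it lies within the listed levels, DeLong is the only test offered for it, and with few added markers the test almost never rejects. The logistic regression could supply a valid test of added terms, but the plan does not give it that role. The missing optimism correction does not depend on which pairs are compared.

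**Conclusion.** The point holds conditionally. If DeLong is applied to fitted nested models, its error rate is wrong in a direction set by the number of added markers, which the plan leaves open. Confidence is high in the statistical behaviour and moderate that nested comparisons are intended. The sizes rest on assumed panel sizes, predictor distributions and base AUROCs.

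A reader might infer a general inflation of false positives, since 20 useless markers would give about 65%. The documents do not support that: no section gives such a panel, about eight markers are named, and with few markers the error runs the other way. Nor is the association analysis of length of stay touched. Optimism is small at the WP1 size. It matters more at about 200 patients, but length of stay is only a secondary endpoint in WP2.

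Severity is minor to moderate: a cheap improvement.

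**What to change.** In Overall outcome analysis:

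- List the pairs of curves or models to be compared, and prespecify the biomarker panel.
- Keep DeLong for raw single markers and other scores fixed in advance, such as the Clinical Frailty Scale or Braden. Do not apply it to fitted models.
- Test added value in nested logistic models with one likelihood-ratio test of the added biomarker block. State how it is pooled if imputation is multiple.
- Report AUROCs and AUROC differences of all fitted models, nested or not, as bootstrap optimism-corrected estimates. Repeat the imputation and any variable selection in each resample.
- State that the correction is only partial at about 200 patients.

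A simple split sample is not a substitute. Fitting on one half and applying DeLong to the other, with five useless markers, rejected 16.2%, nearly all in favour of the smaller model.

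Cost: wording and a little computing time, with no new data. At n=1100 reported AUROCs fall by about 0.007 for an eight-predictor base and 0.015 with eight useless markers added. Non-nested fitted models would have no formal test. Interval coverage for the corrected difference was not examined, so no interval method is proposed. At n=200 the likelihood-ratio test is itself somewhat liberal with eight markers (7.1% to 8.2%), which favours a small panel there. Multiplicity across single markers is a separate matter.

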## **Methods**

Blood tests are standard clinical procedures and will be performed by trained personnel.

For the measurement of muscle strength and function, validated tests will be used and will be performed by trained physiotherapists associated with the study. Measurement of total and regional body composition are standard methods at Bispebjerg-Frederiksberg Hospital and will also be performed by trained physiotherapists associated with the study.

Questionnaires are validated and will be carried out by healthcare professionals associated with the study.

- *Blood tests:* Blood from a peripheral vein (50 ml) will be examined for inflammatory biomarkers, sex hormones, immune activation (suPAR) as well as biomarkers of muscle atrophy and muscle wasting (GDF11 and GDF15).
- *Maximal muscle strength:* Maximal hand grip strength will be measured by a hand-held dynamometer.
- *Functional tests:* Habitual and maximal gait speed and sit to stand test for 30 seconds.
- *Questionnaires:* A frailty score will be assessed by the CSHA Clinical Frailty Scale, the risk of pressure ulcers will be assessed by the Braden Scale, sarcopenia will be assessed by SARC-F, cognitive status by the Orientation-Memory-Concentration test (OMC) and the degree of multimorbidity will be assessed using the Charlson Comorbidity index. Participants included in WP2 will have an additional geriatric assessment as part of clinical practice, including the Barthel Index and the De Morton Mobility Index (DEMMI).
- *Anthropometry:* All subjects will have their body composition calculated by Bioelectrical Impedance Analyses (BIA) at admission. Patients from geriatric rehabilitation care will have an additional BIA measurement at discharge to evaluate the change in body composition during hospitalization. Weight will be assessed using chair scales. Height will be estimated with patients lying in a supine position by a segmometer using knee-height measurement and age using the equation from Chumlea et al (72).

## **Risks, side effects and disadvantages**

The potential discomfort from having a blood test is very brief and rarely cause a small blood accumulation (bruise), which will disappear within a few days. The total amount of blood collected is 25-50ml, which is a quite modest amount compared to the amount collected as a blood donor (500 ml). There are no risks or discomfort associated with assessments of muscle strength or muscle function or by body composition analyses by BIA.

## **Ethical considerations and dissemination of results**

All procedures will be conducted according to “Good Clinical Practice” standards, regarding initiation, monitoring and reporting. All protocols will be submitted for approval by the local ethics committee and Danish Data Protection Agency before trial-initiation and the project will comply with the regulations of the General Data Protection Regulation (GDPR) and the Data Protection Act. Findings from the project, regardless of the outcome, will be published in relevant peer-reviewed scientific journals and positive, negative or inconclusive results will be published on [www.clinicaltrials.gov](http://www.clinicaltrials.gov). Subjects will be anonymous.

The project is expected to provide insight into the biomarkers associated with changes in muscle mass, strength and function in acutely ill older patients and to elucidate the role of a variety of biomarkers on length of hospital stay, readmissions and mortality. Each subject will gain knowledge regarding their physical function and body composition, and patients admitted to geriatric rehabilitation will gain additional knowledge regarding their muscle function. Furthermore, the gained insight into biomarkers of changes in muscle mass and function during hospitalization and their association with length of hospital stay, readmissions and mortality, might prove beneficial for future geriatric patients. The project entails minimal discomfort and no permanent side effects; thus, it is considered ethically sound. All subjects are covered by Bispebjerg-Frederiksberg Hospital patient insurance.

The results will be available following the end of the project with a subsequent period of data processing. As such, individual participant results will not be available immediately following examinations. However, participants will be informed of individual preliminary results, to the desired extent.

